Objectives	
In ten patients with chronic pain refractory to standard medical treatment, we will implant DBS electrodes in brain regions related to pain processing (phantom limb, spinal cord injury and post-stroke pain patients implanted in cingulate and orbital frontal cortex). We will connect these electrodes to an implantable pulse generator that stores field potential data in addition to delivering stimulation (Medtronic Activa PC+S). At multiple time points post-implantation (in our clinic and the patient home), we will record LFP data in conjunction with data regarding pain states. We will also record LFP data in conjunction with quantitative sensory testing (QST) of pain thresholds. Together, these data collections will allow us to identify neurophysiological correlates of pain and then use these signals to set stimulation parameters to disrupt pain-related neural activity, thereby reducing pain states for patients.
 
Hypotheses:
 
 1) Local field potentials recorded using DBS electrodes can predict the transition to an elevated pain state. 2) Open-loop stimulation in response to elevated pain states will reduce duration and/or intensity of the pain state. 3) Closed-loop stimulation may be more effective in treating pain symptoms than open-loop stimulation owing to temporal targeting and avoidance of potential side effects.
Patient Population	
Study subjects will be adults with refractory chronic neuropathic pain.
 
Inclusion Criteria.
 
 • Age ≥ 21 years • Clinical diagnosis of post-stroke pain (thalamic pain), spinal cord injury or phantom limb pain with allodynia or dysesthesia with pinprick anesthesia or hypoesthesia on the affected hemibody or limb (anesthesia dolorosa). • For Post-Stroke Pain: Stroke of ischemic etiology only. MRI done within one year of the first visit showing a lesion that involves the contralateral brainstem, thalamus or cortex. The lesion will involve cortical-subcortical areas in topography consistent with sensory thalamocortical connections. This will include patients with infarcts in the territory of the middle cerebral artery or those with cavernous malformations. A more recent MRI may be required if the patient's condition changed within the previous year.

- For Phantom limb pain: MRI done within one year not showing any contraindication to surgery such as mass, lesion, hemorrhage or other abnormality near target

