In phase 1, patients will be implanted and undergo long-term ambulatory monitoring of their self-reported pain states along with recordings of LFPs from electrodes implanted in the cingulate and orbitofrontal paired regions (~6 months in duration, time period based on previous pain studies [2, 85], visits 6-10, approximately 1 visit per month, up to 10 visits, if needed). Neural activity from implanted electrodes will be simultaneously recorded, one lead per recording channel. During this time period, neural data in combination with pain state reports will be analyzed in order to identify biomarkers of the pain experience and develop a predictive model of increased pain. Importantly, although recruitment will only include patients who are treatment-resistant to pain medication, patients will likely be on medication regimens for pain relief. These will continue to be managed by the patient’s regular pain management team (i.e. will be independent of this study). We will closely monitor the medication regimen and any changes to the regimen. Patients will be asked to record activities at least 3 days a week at the following times:

- Immediately after waking up in the morning
- 30 mins post medication use
- afternoon between 1200 - 1400 pm
- immediately before bedtime

Also, twice a week, patients will be asked to record during pre-identified activities that exacerbate pain (e.g. bending, climbing stairs, etc.). Patients will also be asked to wear a FitBit or similar activity monitor and upload their anonymized data (i.e. no personal health information shared).

Phase 1 – In-clinic sessions

In clinic sessions will also occur in Phase 1, occurring approximately every 3 weeks, taking the measures of VAS pain, VAS unpleasantness, C-SSRS, BDI/BAI, Neuropathic Pain Questionnaire, NIH PROMIS Global health and physical function scales and SF-36. Baseline LFP recordings will also be taken from ~2 minutes. At the study visits from week 3 onwards, we will also include

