A predictive biomarker of pain will be discovered in phase 1 from data collected with at-home and in-clinic recording sessions. This biomarker discovery will be implemented in Phase 2. In phase 1, if data of sufficiently high quality is collected before the 6-month phase period ends, and a predictive biomarker is found before the 6-month phase period ends, the patient can accelerate to the next phases of the study to help ensure a rapid positive clinical outcome.

Phase 2

In the first two weeks of Phase 2, patients will be seen daily for up to two weeks to optimize DBS parameters (visits 11-24), based on biomarker discovery from Phase 1. EEG may be used during this phase for safety, to ensure that subclinical seizure activity is not present during stimulation. If data-collection during the initial two-week period is curtailed for any reason, additional DBS optimization visits may be scheduled so as to sufficiently optimize the biomarker and stimulation settings to enable closed-loop stimulation.

Patients will then have closed-loop stimulation enabled for at-home stimulation, with follow-up clinic visits scheduled every 3 weeks. Stimulation will be enabled or disabled in an ON/OFF state with patient blinded to stimulation status to test for potential placebo / sham effects. In addition to at-home reporting (similar to Phase 1), efficacy of stimulation will be tested every three weeks in-clinic. Additional in-clinic testing of stimulation-related analgesia efficacy and mechanism of action will be done using acute administration of intranasal (4mg/0.1ml, up to two doses), intramuscular (0.4mg/1ml) or IV naloxone (0.4mg/1ml), or saline as control. Study team will assist in administering naloxone before and during analgesic stimulation ON/OFF. Patients and study team will be blinded to what is being provided. Patients who are participating in pain management using opioids will be excluded from performing this study procedure. Phase 2 will last approximately 6 months in duration, time period based on previous unpublished observations in human Parkinson's

patients from our group [143] and published non-human primate observations [58]. Phase 2 in-clinic visits occurring every 3 weeks will test the following:

- 1) VAS pain, VAS unpleasantness, C-SSRS, BDI/BAI, Neuropathic Pain Scale, NIH PROMIS Global health and physical function scales, and SF-36
- 2) Baseline LFP
- 3) Stimulation off + QST (no pain medication)
- 4) Stimulation on + QST (no pain medication)

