V10:01.2019	(Every 6 weeks, +/- 10 days), Months 13-24 (PHASE 3)	Clinical: visit 32 and 36 and final visit of study: H&P for stability Research: visits 32-41: Activa Data collection and VAS scores before and during stimulation, (including QST+baseline LFP recording), recording with painful activity, pain medication; (including QST), recording with painful activity, pain medication. C-SSRS/BDI/BAI/ NIH PROMIS /NPQ, SF-36. DBS open vs closed Final Research visit: Post-intervention Neuropsychological / Behavioral testing	Phase 3: Months 13-24; visit every 6 weeks, 8-10 visits

*Abbreviation: C-SSRS=Columbia Suicide Severity Rating Scale; BDI=Beck Depression Inventory; BAI=Beck Anxiety Inventory.

Progression of phases: We anticipate approximately 6 months for phase 1, a time period based on previous studies [2, 85]. As phase 2 may provide a potential for therapeutic relief of pain symptoms, if patients' pain signatures are reliably detected in a shorter time period in phase 1, the patient may opt to proceed to phase 2 at an earlier time point (i.e. fewer sessions for phase 1). If data of sufficiently high quality is collected before the 6 month phase period ends in Phase 2, depending on pain relief symptoms, the research team may accelerate phase 2 to phase 3 before the 6-month period ends to ensure rapid positive clinical outcomes (in which longer pain relief may occur).

In certain patients who do not experience a sufficiently wide range of pain fluctuation scores (ie. Pain ranges always from 8-9 /10) , it may be difficult to create a predictive model of pain from neural data during phase 1. In these cases, we may opt to proceed to phase 2 at an earlier time point, as soon as 6 weeks post-implantation. Using potentially therapeutic stimulation of ACC or OFC to decrease pain scores at the start of phase 2, we can then aim to calculate biomarkers of pain relief and elevated pain states at the start of phase 2 during stimulation optimization. Additionally, if in phase 1 we anticipate difficulty in successfully collecting biomarker information for any reason, we may opt to progress to phase 2 at an earlier time point to support a positive clinical outcome for the patient.

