LFP data will be analyzed using wide spectrum power-spectral analysis as well as using specific frequency domain for mean log power (i.e. in the delta, theta, alpha, beta, gamma bands). We will also examine coherence and cross-frequency coupling between the channels [145-147]. Using a repeated measures ANOVA statistical analysis, summary statistics for power in relevant frequency bands, pain-related power changes, and indices of phase-amplitude coupling will be compared at different time points, different DBS conditions (on and off), possible medication states (on and off) and different pain states. Although the sample size is small, we will assess the correlation between pain and non-pain states with brain physiology measures, and clinical instruments used to measure pain relief produced by DBS. Additionally, bootstrapping statistical applications (i.e. a Monte Carlo algorithm) and general linear mixed models can be utilized to investigate potential statistical effects, given the small sample size.

Neural activity will be compared during pain states, activity states, medication states, etc. for Phase 1 (no-intervention), as well as Phase 2 (sham controlled and open-loop stimulation) and Phase 3 (open-loop stimulation and closed-loop stimulation).

Sample size calculation: This is a pilot study consisting of existing chronic brain recording technology. The goals are to provide pain relief strategies using the Activa PC+S neural interface, as well as assess feasibility and to collect data that will be used to inform treatment plans using DBS mechanisms. Thus, there is no formal sample size calculation. However, the study is designed such that patients will serve as their own controls in a blinded, placebo versus active open-loop stimulation design, with multiple periods of placebo versus active stimulation. Patients will also serve as their own controls in open-loop versus closed-loop stimulation, in a randomly assigned, blinded, multiple 6-week time periods of open-loop versus closed-loop stimulation. At-home recording sessions will also be utilized to increase the number of testing samples per patient over the trial. In this manner, the statistical power is increased to show treatment efficacy in either of these phases.

Criteria for study success that would justify a larger subsequent trial: This study will be considered to justify a larger subsequent trial if we can demonstrate that:

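### Hypothesis 1 promises a predictive pain biomarker, but the listed LFP analyses test only association, with no out-of-sample check, multiplicity control or criterion for a biomarker being found

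*Combined protocol and SAP*

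**What the plan says.** The Synopsis (Objectives, Hypothesis 1) states: "Local field potentials recorded using DBS electrodes can predict the transition to an elevated pain state". Section 1.0 (Phase 1) says that the recordings and pain reports will be used to "identify biomarkers of the pain experience and develop a predictive model of increased pain".

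Section 6.0 describes the LFP analysis. It lists spectral power in five bands, coherence and cross-frequency coupling, and then: "Using a repeated measures ANOVA statistical analysis, summary statistics for power in relevant frequency bands", along with power changes linked to pain and coupling indices, are to be compared across time points, stimulation conditions, medication states and pain states. It adds "we will assess the correlation between pain and non-pain states with brain physiology measures", and that "bootstrapping statistical applications (i.e. a Monte Carlo algorithm) and general linear mixed models can be utilized to investigate potential statistical effects".

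Two sentences give the biomarker consequences for phase timing. Section 1.0 allows a patient to move on early if the data are good enough and "a predictive biomarker is found before the 6-month phase period ends". Section 3.0 (Progression of phases) allows it if "pain signatures are reliably detected in a shorter time period in phase 1". Neither condition is defined. Section 3.0 also has the marker of a pain state trigger closed-loop stimulation, within limits set by a clinician.

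**The concern.** A difference in mean band power between pain states, or a correlation with pain, shows association in the recordings examined. It does not show how well a marker would identify elevated pain in recordings not yet seen, which is what Hypothesis 1 claims and what closed-loop stimulation needs. Three features of the plan widen the gap: many candidate features, recordings several times a day that are likely to be serially correlated, and no separation between data used to choose a feature and data used to assess it.

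A spurious marker would give a false answer to Hypothesis 1. It would also mean that closed-loop stimulation was timed by noise. A Phase 3 finding of no advantage over open-loop could then reflect a failed marker or a failed principle, and Hypothesis 3 could not be settled.

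**Working it through.** **The plan's own count.** Section 6.0 gives 168 home pain scores per condition in Phase 2. Per week: 3 × 4 + 2 × 1 = 14. Per condition: 14 × (4 periods × 3 weeks) = 168, which reproduces. No count, error rate or accuracy target is given for the biomarker.

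**Inputs from the documents**
- About 14 home recordings a week (Section 4.0). Over 24 weeks, 14 × 24 = 336. Section 3.0 places home downloads from week 3 to month 6, which gives 14 × 23 = 322. Home collection is optional, and clinic visits add about 6 to 8 recordings each.
- Five bands (Section 6.0). Two channels (Section 3.0) give 5 × 2 = 10 features. A bilateral implant has four leads (Section 1.0), giving 5 × 4 = 20. Coherence and coupling indices would add to either, but their number is not stated.

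**Assumptions.** Tests are done per patient at the 5% level, since neither alpha nor a multiplicity rule is stated for this analysis. Features are independent of each other and of pain. Features and pain are first-order autoregressive, and pain is split at its median.

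**Step 1, independent recordings.** The chance of at least one false hit is 1 − 0.95^m.
- m = 10: 1 − 0.95^10 = 0.40.
- m = 20: 1 − 0.95^20 = 0.64.
- At least one of 10 patients, m = 10: 1 − 0.95^100 = 0.994.

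**Step 2, serial correlation.** Simulated patients with no true relation, 336 recordings, a t-test per feature, and a linear discriminant model assessed in-sample and on the last third after fitting on the first two-thirds:

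| Features | Any feature significant, at serial correlation 0 / 0.5 / 0.8 | In-sample AUC, range over the three | Held-out AUC |
|---|---|---|---|
| 10 | 41% / 66% / 95% | 0.59 to 0.67 | about 0.50 |
| 20 | 62% / 88% / 100% | 0.64 to 0.74 | about 0.50 |

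**Step 3, sensitivity.**
- With 10 features correlated 0.5 with each other, the false-hit rate falls to 29% and 52% at serial correlation 0 and 0.5.
- If only the single best feature is used (322 recordings, 10 to 40 features, serial correlation 0 to 0.6), its in-sample AUC in noise is 0.55 to 0.59.
- A Bonferroni correction alone does not repair this. With 20 features and 336 recordings it leaves 19% and 86% false findings at serial correlation 0.5 and 0.8, because each test still treats the recordings as independent.
- For the same reason, a naive two-sided 5% test on held-out data passes a noise marker in the right direction in up to about 9% of patients at serial correlation 0.6, against a nominal 2.5%. The held-out test therefore needs blocks.

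**The case against.** The strongest reply is that the plan nowhere says a biomarker will be accepted by ANOVA or correlation. The predictive model is promised separately with no method named, Section 6.0 also lists bootstrap and mixed models, and mixed models could handle serial correlation. On this view, validation is merely unwritten. The first part stands: a reader might infer that ANOVA is the acceptance test, and the documents do not say so. But every listed LFP method concerns association, the optional ones are not described as validation, and no criterion is stated anywhere. The gap remains.

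Other points in the plan's favour also stand.
- A reader might infer that a found marker triggers progression. Section 1.0 only permits acceleration, and also requires good data; Section 3.0 allows progression without a marker.
- The six-week route in Section 3.0 is for patients whose pain varies too little for a model to be built easily. It should not be read as the earliest biomarker-driven progression.
- This is a pilot, and its LFP success criterion is recording quality. Even so, finding the neural correlates of pain is its first primary objective.
- Twenty features fits a bilateral implant, or assumed coupling indices with a unilateral one. Ten is the figure the documents support for two channels.

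**Conclusion.** The concern holds in this form: prediction is promised, only association is analysed, and no out-of-sample check, multiplicity control or acceptance criterion is given. In noise, a false hit in a given patient has a probability of about 41% to 95% with 10 independent features and 62% to 100% with 20, over serial correlations of 0 to 0.8. It is lower if features are correlated. These figures rest on the assumed alpha, feature counts, independence, recording count and serial correlation. They show that a marker in noise is likely under many settings, not that one is certain.

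A reader might also infer that a spurious marker would create a false pain benefit. The documents do not support that: Phase 2 compares stimulation ON and OFF in randomized periods with the patient blinded, and that contrast does not depend on the marker being valid. The damage falls on Hypothesis 1 and on the interpretation of Hypothesis 3.

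**What to change.** In Section 6.0, add a test of Hypothesis 1 for each patient.
- Define the elevated pain state and the candidate features before evaluation.
- Fit the model on the earlier Phase 1 recordings, for example the first two-thirds by calendar time, and evaluate it on the untouched later part. Alternatively, use time-blocked cross-validation with feature selection inside the folds.
- Report held-out AUC with a block-permutation p-value or a block-bootstrap interval. Claim a predictive biomarker only if held-out performance exceeds chance.
- Keep ANOVA and correlation as descriptive, and report each patient's Phase 3 result beside that patient's held-out performance.

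This test should govern the scientific claim only. It should not be tied to phase acceleration or to the start of stimulation. Separately, the sponsor should reconcile the progression wording in Section 1.0 (data quality and a found biomarker) with that in Section 3.0 (reliable detection, or progression without a marker).

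The cost is analysis work, with no new visits or patients. The downside is fewer recordings for training and low power when Phase 1 is short. In simulation with 20 features and one true marker of AUC 0.70, a held-out test confirmed it in about 16% to 21% of patients with 84 recordings and 68% to 90% with 336. Failure to confirm in a short Phase 1 is therefore not evidence that no marker exists. The model can be refitted on all the data afterwards.

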	
 • MRI (done within one year of the first visit) with significant abnormalities other than those associated with the neurological disorder causing chronic pain. • Implantable hardware not compatible with MRI or with the study. • Inability to comply with study follow-up visits • Previous ablative intracranial surgery for the management of the thalamic pain syndrome. • Previously implanted with deep brain stimulation system or any previously implanted device treatment involving brain stimulation • Major neurological disorder other than the one that led to the chronic pain including epilepsy, neurodegenerative condition or any history of seizure • Requires diathermy, electroconvulsive therapy (ECT) or transcranial magnetic stimulation (TMS) to treat a chronic condition • Has an implanted electronic device such as a neurostimulator, cardiac pacemaker or medication pump • Allergies or known hypersensitivity to materials in the Activa PC+S system (i.e. titanium, polyurethane, silicone, polyetherimide, stainless steel). • Pregnancy or lack of regular use of contraceptives. Patients who become pregnant after enrollment may be excluded from the study. Patients who become pregnant prior to the surgical implantation of the DBS systems will be excluded from the study. • Patients may be excluded from enrollment due to a condition that, in the judgment of the PI, significantly increases risk or reduces significantly the likelihood of benefit from DBS.
Sample Size	10 patients
Efficacy Assessments	Primary Endpoints 
 • Pain intensity / relief visual analog scale • Thermal pain threshold testing with QST Secondary Endpoints 
 • Neuropathic Pain Questionnaire • NIH PROMIS Global health and physical function scales • SF-36

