4.0 Clinical Measurements

Primary

Clinical ratings of pain will be measured by visual analog scales for pain as well as unpleasantness of pain sensation (i.e. “how much pain are you in right now?” and “how much is the pain bothering you right now?”). Patient reports of sensory and pain detection using the Quantitative sensory testing (QST) with the Medoc device will also be used, with and without stimulation.

Physiological measurements related to neural oscillatory activity during various triggered neural recordings with various pain states, activity states, medication states, etc. (~14 recordings per week at home, ~6-8 recordings per in-clinic visit,) will include: wide spectrum power-spectral analysis as well as using specific frequency domain for mean log power (i.e. in the delta, theta, alpha, beta, gamma bands), pain-related changes in broad spectrum power density, and coupling between the phase of low frequency rhythms and broadband gamma amplitude (phase-amplitude coupling, abbreviated PAC) [145-147].

Clinical measures and physiological measurements will be collected and recorded by members of the research and clinical team, as well as from at-home data collection sessions.

Secondary

Measures from Neuropathic Pain Questionnaire, Beck Depression and Anxiety, NIH PROMIS Global health and physical function scales and SF-36 will also be compared from pre-intervention to post Phase 1, phase 2 and phase 3 time points.

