6.0 Statistical Methods and Data Analysis

Ratings of pain will be measured by visual analog scales for pain as well as unpleasantness of pain sensation (i.e. “how much pain are you in right now?” and “how much is the pain bothering you right now?”). Patient reports of sensory and pain detection using the Quantitative sensory testing (QST) with the Medoc device will also be used, with and without stimulation.

In Phase 2, patients will serve as their own controls in a single-blinded phase (6-months in duration) in which placebo versus active open-loop stimulation is used. During this 6-month period, four sham and four active stimulation periods will occur in a random, blinded assignment. During the 8 in-clinic visits, the threshold for sensory and pain detection with the Medoc device will be used and scores will be compared for each patient during sham versus active stimulation periods in one-sample, two-tailed t-test. The 10 patients’ sham versus stimulation scores will also be used in group analysis to test the effects of open-loop and closed-loop stimulation.

In Phase 2, the visual analog scale scores recorded during the at-home recording sessions for various activities will be compared for each patient [(see Figure 3; 168 scores for sham sessions and 168 scores for active stimulation sessions, per patient); (i.e. 3 times per week for 4 activities and 2 times per week for at least 1 painful activity, for at least 14 VAS scores per week; 24 weeks total with 3 weeks per session-sham or stimulation, 8 sessions total, 4 sham sessions and 4 stimulation sessions)].

Multiple regression analysis of all patients will also be used to test for effects of stimulation on various activities, time of day, stimulation effects over time in trial and potential differences in stimulation effects on pain etiologies (i.e. spinal cord injury versus phantom limb versus post-stroke).

Phase 1 (no-intervention) VAS scores will be compared to Phase 2 (sham controlled and active stimulation) VAS scores.

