- 1) Chronic LFP recordings are of adequate quality to assess the LFP signatures of elevated pain.
- 2) No permanent serious adverse events occur (such as trauma with long-term motor deficit).
- 3) Using the Nexus System, therapeutic benefit from stimulation can be demonstrated (i.e. cessation of a pain episode or decreased pain symptoms).

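### The only efficacy go-criterion names no comparator, measure, size or number of patients and is not tied to the randomised sham contrast, so stimulation with no effect could meet it

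*Combined protocol and SAP*

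**What the plan says.** The success criteria close Section 6.0 and open with "This study will be considered to justify a larger subsequent trial if we can demonstrate that". Three items follow. The first is about whether the brain recordings are good enough to study pain signatures. The second is about lasting harm: there must be no serious adverse event that is permanent. The third, which is tied to use of the Nexus device, is that "therapeutic benefit from stimulation can be demonstrated (i.e. cessation of a pain episode or decreased pain symptoms"). Only this last item concerns efficacy.

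Earlier in Section 6.0, the Phase 2 analysis states that "four sham and four active stimulation periods will occur in a random, blinded assignment". It plans per-patient comparisons of sham with active periods and a group analysis, but gives no model, deciding measure or success threshold for the group analysis. It also plans to compare VAS scores from Phase 1, without stimulation, with those from Phase 2. The sample size paragraph states "Thus, there is no formal sample size calculation" and relies on patients acting as their own controls under blinding.

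The outcome lists differ. The synopsis gives "Pain intensity / relief visual analog scale" and thermal pain thresholds as primary. Under its primary heading, Section 4.0 has "Clinical ratings of pain will be measured by visual analog scales for pain as well as unpleasantness of pain sensation", then sensory testing and neural recordings.

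**The concern.** A go rule should be hard to satisfy when the treatment does nothing. Criterion 3 explains benefit as an episode ending or symptoms decreasing, and several features of the design can produce either without any stimulation effect:

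- Entry requires average pain above 5 on a 0-10 scale (synopsis and Section 2.0), so later scores can regress towards the mean.
- Section 3.0 times Phase 2 sessions to each patient's predictable pain peaks and begins them in elevated pain. An episode caught near its peak may subside by itself.
- The Phase 1 versus Phase 2 comparison has no concurrent control, and the wording of criterion 3 would admit it.

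The randomised sham periods exist to separate stimulation from such changes, but the criterion does not mention them. Section 7.0 sets a numeric threshold for worsening pain (more than 25%); there is no counterpart for benefit. At stake is whether the decision to go on to a larger brain-implant trial depends on stimulation doing better than sham.

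**Working it through.** **The plan's own figure.** Section 6.0 gives 168 VAS scores per condition per patient in Phase 2. Scores per week: 3 × 4 + 2 × 1 = 14. Over 24 weeks split equally: 14 × 24 / 2 = 168. This reproduces. There is no power figure to reproduce.

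**Inputs from the plan.** 10 patients; four active and four sham periods of 3 weeks each; two-tailed testing.

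**Assumptions, not in the plan.** Significance level 0.05; patients independent; with no effect, each patient's active mean is equally likely to lie above or below the sham mean. Further assumptions are marked below.

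**Chance of meeting criterion 3 alone when the true effect is zero, by reading:**

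1. Group active-versus-sham contrast significant in the favourable direction: 0.05 / 2 = 2.5%.
2. At least one patient significant in the favourable direction against sham: 1 − 0.975^10 = 22% if scores within a patient are independent. The plan names a per-patient t-test for the sensory thresholds; for VAS it says only that scores are compared for each patient. If 168 versus 168 VAS scores were tested as independent while scores in the same period were correlated at an assumed 0.05 / 0.1 / 0.3, simulation (20,000 runs) gives a favourable result in 12.9% / 19.3% / 30.0% of patients. Then 1 − (1 − p)^10 = 75% / 88% / 97%.
3. Any fall in the group mean, active versus sham: 50%.
4. Any decrease in at least 5 of 10 patients: binomial tail with p = 0.5, 62%.
5. Any decrease in at least 1 of 10 patients: 1 − 0.5^10 = 99.9%.
6. Any fall in the group mean from Phase 1, with an assumed nonspecific improvement of 0.25 / 0.5 / 0.8 SD of change: Φ(d√10) = 79% / 94% / 99%.
7. An episode that ends by itself during stimulation in at least one patient, at an assumed chance of 10% / 30% per patient: 1 − 0.9^10 = 65%; 1 − 0.7^10 = 97%.

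**All three criteria.** At an assumed permanent serious adverse event risk of 1% / 3% / 5% per patient, the chance of none in 10 is 0.99^10 / 0.97^10 / 0.95^10 = 90% / 74% / 60%. Even on reading 5, the chance of a wrong go is therefore at most about 90% / 74% / 60%, before recording quality is considered.

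**If the criterion is tied to sham through a CI.** Using one active-minus-sham difference per patient, the 95% CI half-width is t(0.975, 9) / √10 = 2.262 / 3.162 = 0.72 SD of those differences. Power from the noncentral t distribution, at standardized paired effects of 0.5 / 0.8 / 1.0, is 29% / 62% / 80% with 10 patients and 23% / 50% / 68% with 8.

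**The case against.** The strongest reply is that criterion 3 asks for benefit from stimulation to be demonstrated, which is the language of attribution. The sample size paragraph just before the criteria says efficacy is to be shown with patients as their own controls in a blinded comparison with placebo, and the sham analyses are planned. On that view the bracketed words describe the form benefit takes, the comparator is understood, and the chance of a false success is 2.5%.

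That reading is available, and it limits what can be claimed. A reader might infer that inert stimulation would still lead to a larger trial. The documents do not support this: nowhere do they say that one patient, or any numerical decrease, is enough, and two other criteria must also be met. A reader might also count around ten outcome measures and infer a 40% false-positive risk from 1 − 0.95^10. That figure counts errors in both directions (the favourable one alone gives 1 − 0.975^10 = 22%), assumes independence, and includes measures that are not pain symptoms.

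The sham-based reading is still not written into the criterion. The bracket explains benefit without sham, and the planned group analysis has no deciding measure or threshold. Even a per-patient sham reading leaves 22% or more.

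It is also fair that this is a declared pilot. The lack of a sample size calculation is not a fault, and requiring a CI that excludes zero with 10 patients would miss many real effects.

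**Conclusion.** The concern holds as a should-fix. Criterion 3 is the only efficacy condition in the go rule, and as written stimulation with no effect could meet it. The chance of meeting it with zero effect runs from 2.5% through 50% to 99.9%, depending on a reading the text leaves open. The upper figure is the loosest reading of one criterion out of three and should not be quoted as the chance of a wrong decision.

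The 2.5% rests on an assumed two-sided 5% level. The 50% and 99.9% need only symmetry under no effect and, for 99.9%, independent patients. The figures for correlated scores, nonspecific improvement, self-ending episodes and adverse event risk are illustrations over assumed ranges.

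The gap affects the interpretation of the trial and the decision that follows it. It does not affect the data collected or the planned sham comparisons.

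**What to change.** First reconcile the description of Phase 2 active stimulation. Sections 1.0 and 3.0 call it closed-loop; the Phase 2 analysis and sample size paragraphs of Section 6.0 call it open-loop. Until they agree, the contrast is undefined.

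Then reword criterion 3, for example: *Benefit is judged on the Phase 2 mean within-patient difference in VAS pain intensity between randomised active and sham periods (one mean per period, patient as the unit), reported with its 95% CI, against a threshold fixed before unblinding.* The threshold may be a minimum difference, a responder count, or a CI excluding zero. Name VAS relief, unpleasantness, sensory thresholds, LFP measures, single-episode cessation and the Phase 1 versus Phase 2 comparison as supportive only. Because patients may leave Phase 2 early, say how those with fewer than eight periods enter the mean.

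The change needs no new data, only the reworded criterion and the reconciliation. The cost is a criterion that is harder to meet. If a CI excluding zero is chosen, a real standardized effect of 0.5 / 0.8 / 1.0 would be missed about 71% / 38% / 20% of the time with 10 patients. A minimum difference or responder count on the same contrast is an acceptable alternative, provided its false-success rate is stated when it is set.
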